Obstructive sleep apnoea (OSA) in adults has been correlated with the degree of blood pressure elevation above normal and thereby with the increasing risk of hypertension (HT).⁽¹³⁾ Thus, it is internationally accepted that OSA should be considered as a cause of both primary HT and secondary HT.^(1, 6, 7) The evidence has shown that OSA is linked with uncontrolled high blood pressure, more precisely, OSA has a close and strong relationship with RHT⁽¹⁾ and is cited as the most common secondary cause.⁽¹⁴⁾ Further, limited studies indicate, OSA has been associated with cardiac structure and function.⁽¹⁵⁾ However, relatively few studies have identified an association between OSA and TRHT.

It follows that since the severity of OSA is associated with major modifiable risk factors such as obesity and hyperaldosteronism in patients with RHT,⁽¹⁶⁾ reducing OSA through modifying the risk factor/s may be highly beneficial. Treatment for OSA is wide ranging and may include continuous positive airway pressure (CPAP).⁽¹⁷⁾ However, the goal of CPAP intervention is more to reduce symptoms rather than addressing the cause.⁽¹⁸⁾ Furthermore patient compliance is often low, due to the frustrations associated with the CPAP mask.⁽¹⁹⁾ Rather than just focusing on symptomatic management of OSA, it is suggested that new therapeutic strategies, that address OSA and HT simultaneously, may be more effective.⁽¹⁶⁾ In addition to CPAP management for OSA described above, increasing physical activity may be beneficial in treating both OSA⁽²⁰⁾ and BP⁽²¹⁾ as compliance with a prescribed physical activity programme can lead to a reduction in BP, and thereby, a reduction in the number of antihypertensive medications required by patients with HT.^(6, 7, 9, 22)

3. Aim of Study

To investigate the association between true resistant hypertension and high risk of obstructive sleep apnoea in a sub group of individuals diagnosed with resistant hypertension.

4. Objectives

To:

- determine the prevalence of true resistant hypertension (TRHT) measured by 24h ambulatory blood pressure monitoring in Dunedin based individuals with resistant hypertension (RHT);
- investigate the relationship between Epworth Sleepiness Scale scores and sleep fragmentation in the Dunedin based individuals identified with true resistant hypertension (TRHT);
- investigate the association between true resistant hypertension (TRHT) and high risk of obstructive sleep apnoea (OSA), in the Dunedin based individuals

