5. Hypothesis

5a. Primary Hypothesis

H_A: In Dunedin based individuals aged 60 years and below, diagnosed with resistant hypertension, 24h ambulatory blood pressure monitoring will identify a subgroup with true resistant hypertension.

H₀: In Dunedin based individuals aged 60 years and below, diagnosed with resistant hypertension, 24h ambulatory blood pressure monitoring will not identify a subgroup with true resistant hypertension.

5b. Secondary Hypotheses

H_A: There is correlation between Epworth Sleepiness Scale (ESS) score, and levels of sleep fragmentation in the subgroup of individuals with true resistant hypertension

H₀: There is no correlation between Epworth Sleepiness Scale (ESS) score, and levels of sleep fragmentation in the subgroup of individuals with true resistant hypertension

H_A: There is an association between true resistant hypertension and high risk of OSA, in the subgroup of individuals.

H₀: There is no association between true resistant hypertension and high risk of OSA, in the subgroup of individuals.

6. Study Design

The study is a descriptive observational study. The design has been selected to identify those with true resistant hypertension (TRHT) in a population of Dunedin based adults with resistant hypertension (RHT) and to investigate the risk of obstructive sleep apnoea (OSA) in the subset identified with TRHT. The anthropometric characteristics (body mass index (BMI), neck circumference, waist to hip ratio), cardio respiratory fitness (6MWT); quality of life (SF-36); and echo cardiogram parameters of the sub population with TRHT and high risk of OSA, will be determined to describe the study population.

7. Study Setting/ Location

The study is categorised as a single centre study at the University of Otago. The location will be the School of Physiotherapy, University of Otago ([name]). Specific investigations, and interpretation of data downloaded from 24hABPM and Echo-cardiography recordings, will be carried out in the Dunedin School of Medicine Cardiology Research Laboratory, on 9th floor of the Dunedin Public Hospital.

8. Study Population

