The population will comprise adults with resistant hypertension (RHT), based in the Dunedin region, aged 60 years and younger, who have been diagnosed with high blood pressure and are on three or more pharmacological agents of different classes including a diuretic. The population has been drawn from the Ministry of Health Pharmaceutical Collection Warehouse, via the Best Practice Advocacy Centre (bpac),⁽²³⁾ New Zealand.

The total number of adults with hypertension and being pharmacologically managed with three or more antihypertensive medications (estimated RHT) in New Zealand is 100,340; Southern District Health Board, 8425; and in the Dunedin region, 3184. The number of adults 60 years age or below in the Dunedin region with RHT is 559.⁽²⁴⁾

9. Eligibility Criteria

Inclusion criteria

- Age: 18-60 years inclusive
- Gender: all
- Able to communicate/follow instructions in English
- Based in Dunedin region
- Diagnosed with hypertension
- Prescribed three or more antihypertensive medications including a diuretic (RHT definition⁽⁹⁾).

Exclusion criteria

- Diagnosed with hypertension prescribed two or less antihypertensive medications
- Adults above the age of 60 years
- Diagnosed/known renal disease
- Females who are pregnant

10. Study Outcomes

Primary Outcome

The prevalence of TRHT in a population with RHT and the association of TRHT with high risk of OSA.

Secondary Outcome(s)

The correlation between increased Epworth Sleepiness Scale score and sleep fragmentation in the subset with true resistant hypertension.

11. Study Procedures

a. Recruitment of participants

Adults (18-60y) in the Dunedin region, [anonymized] on three or more pharmacological agents of different classes, and the general practices [anonymized] they are enrolled at, have been identified from the Ministry of Health Pharmaceutical Collection Warehouse, via the Best Practice Advocacy Centre (bpac),⁽²³⁾ New Zealand. The number of adults on the list is 559⁽²⁴⁾, [the list of names will remain de-identified to the research team as letters will be forwarded by General Practitioners].

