Following a briefing by researchers about the study at a scheduled meeting of the local General Practitioners Association, researchers will gain agreement from General Practitioners to distribute a letter to their patients identified from PWC database. The letter of invitation to participate in the study will be co-signed by [name] and Associate [name]. Inclusion criteria will be adults 18-60 years, who meet the definition for RHT⁽⁹⁾, have no known renal disease and are able to communicate in English. Based on the population with RHT in Dunedin region a sample size n=83, with 95% confidence interval and 10% margin of error, is required. The recruitment target is n=100 with the dropout rate of up to 20%.

A list of individuals who consent to participate in the study will be created and each will be matched with a random serial number generated by the computer (using MS Excel). NIH number/name and contact details will be included on the database but remain deidentified other than to the research group. The random ID number will be used in the study.

The proposed recruitment period is August 2018 to April 2019; 9 months

Step 1

For individuals identified with RHT.

August 2018 - invitation to participate in the study;

August 2018 – March 2019: initial recruitment, initial measurements, 24hABPM

Step 2

For the sub group identified with TRHT and high ESS score.

September 2018 – April 2019: Echo cardiogram, cardiorespiratory fitness test (6MWT) and 24h day/night activity monitoring for one week

October 2019 September 2020 – write up and publication

11b. Randomisation

The study is a descriptive observational trial.

11c. Study procedure

Step I – Initial recruitment

Potential participants will be invited to contact [name] with enquiries and to indicate their interest in participating in the study. The Principal investigator (PI), the PhD candidate, will provide each participant with an appointment time for the initial assessment where written informed consent will be obtained first. The session will be at the School of Physiotherapy. A summary of the stages of the study is outlined in Figure 1.

Step II – Assessment and measurements

Appointment 1:

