A statistician was consulted to confirm the calculation of the sample size based on the population with RHT in Dunedin region (559). Thus, the sample size is $n=83$, with 95% confidence level and 10% margin of error. The recruitment target is set at $n=100$ and with the dropout rate of up to 20%, the estimated sample size ($n=83$) is expected to be able to be fulfilled.

The cohort with true resistant hypertension and high risk of OSA is unknown for the Dunedin based population with RHT. An 18% response rate will be sufficient to achieve the target sample size ($n=100$) for the study.

12b. Statistical methods

Simple statistics (mean, standard deviation, range) will be used to describe the demographic data and the measurements (anthropometry /blood pressure/ /sleep/activity/cardiac parameters) of the population with RHT in Dunedin region and in the sub population with TRHT and high risk of OSA. The data for anthropometrics, blood pressure, activity and cardiac parameters will be compared with accepted international guidelines,⁽²⁵⁾ and questionnaires will be interpreted using standard descriptors.

The relationship between the anthropometry parameters, blood pressure, ESS score, cardiorespiratory fitness, and activity and sleep levels with TRHT will be determined using regression analysis.

The statistical package for social sciences (SPSS) version 25.0 or above for Windows (IBM SPSS version 25.0 or above), NY, USA⁽¹⁰⁾ will be used for the data analysis.

13. Ethical Considerations

The study to be conducted will conform fully with the principles of the “Declaration of Helsinki”, Good Clinical Practice (GCP) and within the laws and regulations of New Zealand. The study has been registered on the Australian New Zealand Clinical Trials Registry (ANZCTR). Ethical clearance will be obtained from the HDEC, New Zealand prior to commencing the study.

No identifiable information will be used in the study. For the identification of the cohort, the adults in the Dunedin region, who meet the criteria for RHT, on three or more pharmacological agents of different classes, including diuretic, have been identified (by bpac from the Ministry of Health Pharmaceutical Collection Warehouse and categorised to the various general practices. Letters supplied will be sent to those identified from their General Practitioner by linking names and addresses to national health numbers)

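### The primary hypothesis in Section 5a asks only whether any true resistant hypertension exists, while the objective, primary outcome and sample size call for a prevalence estimate

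*Protocol*

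**What the plan says.** - **Section 5a, Primary Hypothesis.** The alternative is that "24h ambulatory blood pressure monitoring will identify a subgroup with true resistant hypertension"; the null is that "24h ambulatory blood pressure monitoring will not identify a subgroup with true resistant hypertension". Neither gives a reference prevalence or a minimum size for the subgroup.
- **Section 4, Objectives.** The first objective is to "determine the prevalence of true resistant hypertension (TRHT) measured by 24h ambulatory blood pressure monitoring".
- **Section 10, Study Outcomes.** The primary outcome is "The prevalence of TRHT in a population with RHT and the association of TRHT with high risk of OSA".
- **Section 6, Study Design.** "The study is a descriptive observational study".
- **Sections 11a and 12a.** The sample size is given as "a sample size n=83, with 95% confidence interval and 10% margin of error, is required", and again as 83 "with 95% confidence level and 10% margin of error", for a population of 559. No power, effect size or null value is given.
- **Introduction and Section 11c, Appointment 1.** Ambulatory monitoring is fitted to the participants with resistant hypertension who score 9 or more on the Epworth scale. The Step 1 timeline in Section 11a lists monitoring for individuals with resistant hypertension and mentions no Epworth condition.

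**The concern.** A null hypothesis is useful if the data could plausibly support either side and if the answer settles the study's question. This one does little of either. Without a reference value, it says that nobody among the participants has true resistant hypertension, and a single case disproves it.

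The rest of the protocol already assumes that it is false. The secondary hypotheses in Section 5b are set within the subgroup with true resistant hypertension. Section 11c schedules echocardiography, a walk test and actigraphy for that subgroup. Sections 11c and 14 plan a second study that draws on it.

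A conclusion reported against Section 5a would be that a subgroup exists. That does not tell the reader whether the condition is rare or common among people with resistant hypertension, which is what the first objective sets out to learn.

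**Working it through.** **1. Reproduce the sample size.** Inputs: 95% confidence and a 10-point margin (Sections 11a, 12a) and population 559 (Sections 8, 12a). The planning proportion is not stated; p = 0.5 is assumed.

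- n0 = 1.96² × 0.25 / 0.10² = 96.04
- with finite-population correction, n = 96.04 / (1 + 95.04/559) = 82.08, rounded up to 83

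The stated 83 reproduces as a precision calculation for a single proportion. The protocol does not say in words that this proportion is the prevalence of true resistant hypertension. That is inferred from the arithmetic and from prevalence being the first objective and the first part of the primary outcome.

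**2. Chance that the null is refuted.** If one case is enough and m people are monitored, the chance is 1 − (1 − p)^m. The protocol gives neither an expected prevalence p nor the number who will score 9 or more on the Epworth scale. Both are therefore shown as ranges, with 20, 30 and 40 assumed for the restricted group.

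| Monitored (m) | p = 1% | p = 2% | p = 5% | p = 10% | p needed for 95% chance |
|---|---|---|---|---|---|
| 83 | 56.6% | 81.3% | 98.6% | 99.98% | 3.5% |
| 40 | 33.1% | 55.4% | 87.1% | 98.5% | 7.2% |
| 30 | 26.0% | 45.5% | 78.5% | 95.8% | 9.5% |
| 20 | 18.2% | 33.2% | 64.2% | 87.8% | 13.9% |

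The last column is 1 − 0.05^(1/m). Sampling without replacement from 559 changes little: with 28 cases in 559 (5%) and 83 sampled, the chance is 99.0%.

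**3. What the verdict cannot distinguish.** Wilson 95% intervals:

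- 1/83 = 1.2% (0.2% to 6.5%)
- 33/83 = 39.8% (29.9% to 50.5%)

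The intervals do not overlap, yet both results refute the Section 5a null in the same way.

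**4. Precision if prevalence is estimated instead.** Half-widths near 50%:

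- 83 assessed, with finite-population correction: 1.96 × √(0.25/83 × 476/558) = 9.9 points
- 83 assessed, Wilson without correction: z√(0.25/m + z²/4m²) / (1 + z²/m) = 10.5 points
- Wilson without correction for 40, 30 and 20 assessed: 14.8, 16.8 and 20.1 points

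The 10-point target is therefore met with 83 people only if the finite-population correction is used. It is not met if monitoring is confined to a group of 20 to 40.

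**The case against.** The strongest reply is that nothing the study does depends on Section 5a. Prevalence is in the scientific title, in Objective 1 and in the primary outcome, and the sample size is built for it. Prevalences of 2% and 60% would be reported differently under the primary outcome whatever Section 5a says. This stands, and it limits the harm.

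A reader might go further than the documents allow in three ways.

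- **That there is a formal primary test almost certain to reject.** Section 12b names no test, significance level or rejection rule for Section 5a. Near-certainty also depends on an unknown prevalence and on how many people are monitored. With 83 monitored at 2% prevalence, there is still a 19% chance of no case. With 20 monitored at 5%, that chance is about 36%.
- **That Section 12b is wrong because it names no estimator for the proportion.** Its sentence "Simple statistics (mean, standard deviation, range) will be used to describe the demographic data" goes on to cover the study measurements and does not claim to be the primary analysis. The choice of interval method can be left to a statistical analysis plan, which is not shown here.
- **That 'subgroup' must mean exactly one person or more.** It could mean several people. The protocol sets no minimum, however, so one case is the natural literal reading, and a small unstated minimum would not make the hypothesis informative about prevalence.

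**Conclusion.** The mismatch is real and lies within the protocol. Section 5a poses an existence question with a null of zero prevalence, while Sections 4, 10, 11a and 12a pose an estimation question. The logical point needs no assumption about prevalence beyond the literal reading of the null: one case refutes it, and the verdict is identical at 1/83 and 33/83.

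How likely refutation is remains conditional. It is at least 95% from about 3.5% prevalence if all 83 are monitored, and from about 7% to 14% if 40 down to 20 are monitored. These group sizes are assumptions.

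Severity is minor to moderate. The wording does not change what is measured or how many are recruited, but it would let the stated primary hypothesis be upheld without answering the study's main question.

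**What to change.** 1. In Section 5a, replace the hypothesis pair with an estimation statement. For example: the prevalence of true resistant hypertension among participants with resistant hypertension will be estimated with a two-sided 95% confidence interval, and the primary conclusion will rest on that interval. Testing against a justified non-zero reference prevalence is an alternative, but the protocol offers no such value.
2. In Section 12a, say that the margin of error refers to this prevalence and state the assumed p = 0.5. Give the precision as it is: with 83 assessed, about 9.9 points near 50% with finite-population correction for 559, and about 10.5 points (Wilson) without it.
3. Reconcile the denominator. The Introduction and Section 11c restrict monitoring to an Epworth score of 9 or more, whereas Objective 1 and the Step 1 timeline in Section 11a refer to people with resistant hypertension in general. Prevalence among the restricted group is not the prevalence in Objective 1, and with 20 to 40 monitored its half-width near 50% would be about 15 to 20 points. The new statement should not be adopted with a denominator of monitoring completers until these sections agree.

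Items 1 and 2 cost wording only and need no new data. Item 3 also starts as a matter of wording, but its resolution determines whether the stated precision can be reached.

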Research Protocol

Study Title

Scientific title: The prevalence of true resistant hypertension in Dunedin based adults with resistant hypertension and the association between true resistant hypertension and obstructive sleep apnoea risk.

Lay title: Identification of adults with true high blood pressure resistant to drugs and its relationship with breath pauses during sleep.

Study Investigator(s)

Principal Investigator: [name]
Ph. [name]/
Email: [contact]

Co-Investigator: [name]

Co-Investigator: [name]

Co-Investigator: Associate [name]

1. School of Physiotherapy, University of Otago, [name].
2. Cardiology Department, Dunedin School of Medicine, University of Otago, Dunedin, New Zealand.

Introduction

This study is an observational study which aims to: 1) identify individuals with true resistant hypertension (TRHT) in a population of Dunedin based adults 60 years and younger, with resistant hypertension (RHT) as defined under the current guidelines (2017) of the American Heart Association and American College of Cardiology; 2) investigate the association between TRHT and high risk of obstructive sleep apnoea (OSA) in the sub group of individuals with TRHT.

Dunedin based adults, 60 years or younger, who meet the criteria for RHT (are on three or more pharmacological agents of different classes, including a diuretic), have been identified from the Ministry of Health Pharmaceutical Collection Warehouse (PCW)

database. Following a briefing by researchers about the study at a scheduled meeting of the local General Practitioners Association, researchers will gain agreement from General Practitioners to distribute a letter to patients. A letter of invitation to participate in the study will be co-signed by [name] and Associate [name]. Letters will then be distributed to General Practitioners, who will be asked to forward copies to their patients identified from the PCW database.

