There is an internationally accepted protocol for the diagnosis of HT (Report of the Joint National Committee on Prevention, Detection, Evaluation and Treatment of High Blood Pressure, JNC 7 Report 2003⁽⁵⁾). Despite the protocol itself being well established, a new guideline for the definition of Stage I hypertension was published in 2017 by the American College of Cardiology/American Heart Association (ACC/AHA).⁽⁶⁾ The New Zealand Guidelines (2018) have been updated to comply with the new definition.⁽³⁾

Stage 1 hypertension is now defined as 130 to 139 mm Hg systolic or 80 to 89 mm Hg diastolic, and Stage 2 hypertension as 140/90 mm Hg or higher,⁽⁶⁾ thus bringing the 'prehypertension' group into the hypertension classification. Importantly management is centered around an assessment and treatment approach based on the cardiovascular risk rather than treating blood pressure as an isolated risk factor.^(3, 6, 7) For Stage 1 HT, management focusses on lifestyle factors in particular, physical activity, diet and reducing stress, rather than pharmacological interventions.^(3, 6-8)

Resistant hypertension (RHT) is a subset of HT. RHT is defined as 'blood pressure above the minimum level for hypertension despite concurrent use of three anti-hypertensive agents of different classes at optimal dose amounts, one of these being a diuretic'.⁽⁹⁾ Use of four medications including a diuretic is also considered as 'resistant' regardless of blood pressure values.⁽⁹⁾ An accurate account of compliance with medication and recorded blood pressure (BP) is important in the diagnosis of RHT to differentiate it from other categories of hypertension such as pseudo-hypertension, white coat hypertension and masked hypertension.⁽⁹⁾ Twenty four hour ambulatory blood pressure monitoring (24h APMB) has been shown to be the most effective and valid tool for diagnosing true RHT (TRHT).⁽⁶⁾ However, a key limitation of many studies that have investigated the management of RHT by focusing on lifestyle changes, such as an increase physical activity, have failed to diagnose TRHT within their cohorts.⁽¹⁰⁻¹²⁾

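### The prevalence denominator is labelled resistant hypertension on drug count alone, so it can include people controlled on three drugs whom the protocol's own definition excludes

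*Protocol*

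**What the plan says.** **Definition.** Section 2 (Background) defines RHT as "blood pressure above the minimum level for hypertension despite concurrent use of three anti-hypertensive agents of different classes at optimal dose amounts", one of them a diuretic. It adds a second branch: "Use of four medications including a diuretic is also considered as" resistant, "regardless of blood pressure values". On the threshold, the same section says "Stage 1 hypertension is now defined as 130 to 139 mm Hg systolic or 80 to 89 mm Hg diastolic".

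**Criterion applied.** The Introduction describes the target group as adults "who meet the criteria for RHT (are on three or more pharmacological agents of different classes, including a diuretic"). Section 8 describes adults "who have been diagnosed with high blood pressure and are on three or more pharmacological agents of different classes including a diuretic". Section 9 requires diagnosed hypertension and "Prescribed three or more antihypertensive medications including a diuretic", and marks this as the RHT definition under the reference that Section 2 cites. None of these asks for raised pressure on treatment.

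**Sampling frame.** The counts come from a national pharmaceutical database. Section 8 describes the wider counts as people "managed with three or more antihypertensive medications (estimated RHT"), then gives 559 Dunedin adults aged 60 or below as having RHT, without that qualifier. Section 12a uses 559 as the RHT population for the sample size. Section 13 again describes the cohort as meeting the RHT criteria by drug count.

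**Procedures.** Section 11a says that participants will meet the RHT definition. Section 11c has office blood pressure taken at Appointment 1, with no cut-off attached. Ambulatory monitoring is then fitted to those scoring 9 or more on the Epworth scale. Section 10 makes the prevalence of true RHT (TRHT) in a population with RHT part of the primary outcome.

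**The concern.** A prevalence is only as well defined as its denominator. Someone whose pressure is controlled on exactly three drugs does not have RHT under Section 2, yet satisfies Section 9 and is counted as RHT. Such a person can add to the denominator and, unless ambulatory pressure is raised, never to the numerator.

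The result would be reported as TRHT prevalence in RHT, when it is really the share with raised ambulatory pressure among users of three or more drugs. The protocol bases its claim to novelty (Introduction and Section 14) on applying the guideline strictly and separating true from apparent resistance, so the label on this group matters to what the study can conclude.

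**Working it through.** **1. Who is classified differently.** All rows assume diagnosed hypertension and a diuretic.

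| Person | Section 2 | Introduction, Sections 8 and 9 |
|---|---|---|
| Three agents, pressure above threshold | RHT (if different classes, optimal dose) | RHT |
| Three agents, pressure controlled | not RHT | RHT |
| Four or more agents, any pressure | RHT | RHT |

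Only the middle row is misplaced. The Section 9 bullet also omits the different-classes condition, which the Introduction and Section 8 keep. No eligibility text carries the optimal-dose condition.

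**2. The plan's own sample size.** Inputs from Section 12a: N = 559, 95% confidence, margin 10 points. The expected proportion is not stated; I assume 0.5.

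- n0 = 1.96² × 0.5 × 0.5 / 0.10² = 96.04
- n = 96.04 / (1 + 95.04/559) = 82.08, rounded up to 83

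The plan's 83 reproduces. The arithmetic is sound, but the 559 in it is a drug-count figure.

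**3. Dilution.** Let π be TRHT prevalence among those meeting Section 2, c the share of the *whole* denominator controlled on exactly three drugs, and m the share of those controlled people with raised ambulatory pressure. None is in the documents.

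Reported prevalence = (1 − c)π + c·m, so the loss = c(π − m).

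With π = 50% and m = 0 (both assumed):

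| c (assumed) | Reported | Loss |
|---|---|---|
| 10% | 0.90 × 50% = 45% | 5 points |
| 20% | 0.80 × 50% = 40% | 10 points |
| 40% | 0.60 × 50% = 30% | 20 points |

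For a given c and π, m = 0 is the worst case. With m = 15% (assumed), the loss at c = 20% is 0.20 × (50 − 15) = 7 points, and at c = 40% it is 0.40 × 35 = 14 points.

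Because four-drug users stay in the definition, c is smaller than the controlled share among three-drug users. If half the participants take four or more drugs and 20% of the rest are controlled (both assumed), c = 0.5 × 0.20 = 10%.

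**4. Precision in the subgroup meeting Section 2.** This takes 83 completers, all with ambulatory monitoring, and shrinks the population by the same share. Margin = 1.96 × √[(0.25/n) × (N − n)/(N − 1)].

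| c | n | N | Margin |
|---|---|---|---|
| 0 | 83 | 559 | 9.9 points |
| 10% | 75 | 503 | 10.5 points |
| 20% | 66 | 447 | 11.1 points |
| 40% | 50 | 335 | 12.8 points |

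These are best cases, since Section 11c gives ambulatory monitoring only to those at or above the Epworth cut-off.

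**The case against.** **The text is less one-sided than it looks.** Section 11a says participants meet the RHT definition and cites the same reference. Section 11c takes office pressure and then speaks of the subset with RHT, which could be read as classifying people at that visit. Figure 1 and Appendix 1 are not available. This stands in part: it cannot be said that office pressure is *never* used to classify RHT, only that no visible step does so. It does not remove the conflict, because the Introduction and Section 9 spell the definition out as a drug count.

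**The dilution is hypothetical and could be small.** This stands. A reader might infer that the bias must exceed the planned ±10 points. The documents do not support that: with π = 50% and c = 20% the loss only equals 10 points when m = 0, and any masked hypertension, a category Section 2 itself names, brings it below.

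**Why not simply make office-pressure-defined RHT the primary denominator?** A reader might infer that this needs nothing new. The documents do not support that either. The number of agents is not listed among the Appointment 1 data in Section 11c or in Table 1, so the four-agent branch may not be applicable from what is collected. Pressure from a single visit would drop people with normal office but raised ambulatory pressure from numerator and denominator alike. And a prevalence in all enrolled cannot be computed, because those below the Epworth cut-off have no ambulatory reading.

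**Conclusion.** The point holds as a mislabelled denominator. Followed as written, the protocol counts people controlled on exactly three drugs as RHT, contrary to its own Section 2, and the primary prevalence describes users of three or more drugs who received ambulatory monitoring.

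The direction is downward whenever controlled people have raised ambulatory pressure less often than those who meet the definition. The size is unknown: at most 5, 10 or 20 points for c = 10%, 20% or 40%, taking π as 50%.

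Two further readings should be resisted. The criterion does not admit anyone on three drugs, since a hypertension diagnosis and a diuretic are also required. And the sample size of 83 is not miscalculated; what needs correcting is the description of the 559 on which it rests. The Epworth gate on ambulatory monitoring is a separate limit on who can be counted.

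**What to change.** 1. Reconcile the Introduction and Sections 2, 8, 9, 11a, 12a and 13, so that one definition is stated and the criterion actually applied is named for what it is.
2. Name the primary denominator, and the 559, as *adults prescribed three or more antihypertensives including a diuretic (apparent RHT)*.
3. Record the number of agents when eligibility is checked.
4. Also report TRHT prevalence in the subgroup meeting Section 2: three agents with Appointment 1 office pressure at or above the protocol's stated threshold, or four or more agents including a diuretic. Report participants controlled on three agents separately. Restrict both to those with ambulatory monitoring, and give the numbers enrolled and monitored.

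**Cost.** Wording changes, one recorded item (unless Appendix 1 already captures it) and one derived variable; no new clinical measurement.

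**Downsides.** The subgroup is smaller and its margin exceeds ±10 points, 11.1 at c = 20% and 12.8 at c = 40% even if every completer is monitored. Office pressure from one visit will misclassify some people in both directions (white-coat and masked hypertension), which is why this result should sit beside the relabelled primary one and not replace it. The optimal-dose condition would remain unverified and should be stated as a limitation.

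### A recruitment target of 100 supports the required n=83 only up to 17% dropout, not the 20% stated in section 12a (minor)

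*Protocol*

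**What the plan says.** Section 8 gives the source population: "The number of adults 60 years age or below in the Dunedin region with RHT is 559". Section 11a sets the requirement: "Based on the population with RHT in Dunedin region a sample size n=83, with 95% confidence interval and 10% margin of error, is required". It then adds the recruitment figures: "The recruitment target is n=100 with the dropout rate of up to 20" (per cent).

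Section 12a repeats the 83, says that a statistician was consulted to confirm the sample-size calculation, and draws the conclusion at issue: "with the dropout rate of up to 20%, the estimated sample size ($n=83$) is expected to be able to be fulfilled". It also says: "An 18% response rate will be sufficient to achieve the target sample size ($n=100$) for the study".

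Section 11a supplies only the inputs. The statement that fails is the one in section 12a. Neither section gives an expected prevalence.

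**The concern.** A dropout allowance exists to protect the required number at the worst loss that the plan accepts. Section 12a says that 83 is safe with losses of up to 20% from 100 recruits, but 20% of 100 is 20, which leaves 80. The three figures (83, 100 and 20%) are the protocol's own, and they do not fit together.

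Precision is the only stated basis for the sample size, and the prevalence of true resistant hypertension is part of the primary outcome in section 10. A team that relied on section 12a could stop recruiting at 100, lose 20, and believe that the requirement had been met.

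**Working it through.** **Inputs.** Population N = 559 (section 8, repeated in 11a and 12a). Confidence 95%, so z = 1.96; margin e = 0.10; required n = 83; target 100; dropout up to 20% (11a and 12a). The proportion p is not stated; p = 0.5, the least favourable value, is assumed.

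**1. Reproduce the required n.** For a single proportion with finite-population correction:

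- n0 = z² p(1 − p) / e² = 1.96² × 0.25 / 0.01 = 96.04
- n = n0 / (1 + (n0 − 1)/N) = 96.04 / (1 + 95.04/559) = 82.08, rounded up to **83**

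The stated figure reproduces. A common variant, n0/(1 + n0/N), gives 81.96, so 82; that is also above 80.

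**2. Check the dropout step.**

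- Retained from 100 at 20% dropout: 100 × 0.80 = **80**, and 83 − 80 = 3 short
- Largest dropout that leaves 83 of 100: 1 − 83/100 = **17%**
- Recruits needed to keep 83 at 20% dropout: 83/0.80 = 103.75, so **104**
- For comparison, 83 × 1.2 = 99.6, which rounds to 100

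The last line suggests that the target came from adding 20% to 83 instead of dividing by 0.80. That origin is an inference, and the shortfall does not depend on it.

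**3. Response rate.** 100/559 = 17.9%, so the stated 18% is right for a target of 100. For 104 it would be 104/559 = 18.6%.

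**4. Effect on precision.** Half-width = z √[ p(1 − p)/n × (N − n)/(N − 1) ].

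| n | p | Half-width (points) |
|---|---|---|
| 83 | 0.50 | 9.93 |
| 82 | 0.50 | 10.01 |
| 80 | 0.50 | 10.15 |
| 80 | 0.40 | 9.95 |
| 80 | 0.30 | 9.30 |

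For n = 80 and p = 0.5: 1.96 × √(0.25/80 × 479/558) = 0.1015. With 80 participants the half-width stays within 10 points when prevalence is at or below about 41%, or at or above about 59%.

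**The case against.** The case for leaving the text alone has four parts.

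- **The 20% is a ceiling, and 83 is only expected.** The statement is true for any dropout of 17% or less. But section 12a makes the claim for the whole range up to 20%, and between 17% and 20% it is false. Nothing elsewhere in the protocol corrects it.
- **Dropout need not mean loss from the prevalence estimate.** Section 11f keeps data collected before withdrawal. Under section 11c the 24-hour monitor is fitted at appointment 1 and read the next day, so someone lost during the later actigraphy week would still count. The protocol does not say when the 20% are lost. This stands: losing all 20 from the estimate is the worst case.
- **The effect is negligible.** Three participants and 0.15 of a point in a descriptive study would change no conclusion. This also stands, and it is why the point is minor.
- **The sample size itself is right.** It is, as step 1 of the working shows.

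Two stronger readings are tempting. A reader might infer that the study misses its ±10% margin. The documents do not support that as a general statement: the miss needs high dropout, full loss of the dropouts and a prevalence between about 41% and 59%, and 10.15 still rounds to the whole-number 10% that the protocol uses. A reader might also infer that the 18% response rate is a second error. It is correct for 100 recruits and changes only if the target changes.

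**Conclusion.** The dropout statement in section 12a is wrong as written: 100 recruits with 20% dropout leave 80, not 83, and a target of 100 supports at most 17% dropout. This rests on the protocol's own figures and needs no assumption.

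The consequence is small and conditional. At the ceiling the shortfall is 3 participants, and the half-width is about 10.15 points instead of at most 10. That holds only if dropout reaches 20%, all dropouts are lost to the estimate, and prevalence is near 50% (p = 0.5 is assumed). The required n=83 and the 18% response rate both stand. Severity: minor.

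**What to change.** Restate in sections 11a and 12a that a target of 100 tolerates dropout of up to 17%. This changes one sentence in each section and needs no extra participants.

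If the 20% allowance is to be kept with n=83, set the target at 104 and change the response rate in 12a from 18% to 18.6%. That costs four more recruits.

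Do not instead write that 80 participants give a margin of ±10.2%. Section 11c gives 24-hour ambulatory monitoring only to participants who score 9 or more on the Epworth scale, so true resistant hypertension would not be measured in all 80. The protocol does not state what share would qualify. As an illustration only, an assumed share of 30% to 50% of 80 would be 24 to 40 people. With p = 0.5 and the population reduced by the same share, the half-width would be about 19 to 14 points. That restriction is a separate matter, but it makes a ±10.2% claim unsafe.
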